2.3 Protocol Purpose

This is a double-blind, randomized, placebo-controlled, dose-finding Phase 2 pilot study designed to explore the safety and the therapeutic potential of MDMA-assisted therapy for treating social anxiety in 12 MDMA-naïve adults on the autism spectrum. This study will provide an estimate of effect size based on response to two experimental sessions of MDMA-assisted therapy in autistic adults on measures of safety, social anxiety, social perception, and psychiatric symptoms in comparison to a placebo control group. The primary outcome measure for the study will be the clinician-administered Liebowitz Social Anxiety Scale (LSAS) administered by a blinded Independent Rater (IR). Self-report measures will correspond to indications that often co-present with autism, including anxiety, stress, depression, emotion regulation, alexithymia, differences in some empathy domains, and other psychosocial challenges. Subjects will receive ongoing social support during the study in the form of non-drug therapy and active involvement of a support partner.

This study will employ biomarker analyses in combination with clinical outcome measures to provide useful insights into the underlying mechanism of MDMA's psychosocial and anxiolytic effects, and to examine any biological differences to treatment responses. The time course of biomarker concentrations will be used to determine if MDMA-assisted therapy causes lasting changes in biomarker levels in comparison to baseline.

Each of the 12 subjects will participate in two blinded experimental sessions, assisted by either MDMA or placebo, of seven hours in duration within a brief course of non-drug therapy, including three hour-long preparatory sessions at the start of the study and three hour-long integrative sessions during the month after each experimental session at two week intervals. This study is designed as a dose escalation study to assist with the exploration of safety and finding the most effective dose in this population. Based on anecdotal reports, subjects in this population may be more sensitive to the standard dose of 125mg MDMA that has indications of efficacy for PTSD [68]. Subjects assigned to the MDMA group will receive two of three different doses, either 75mg, 100mg, or 125mg MDMA. Overall, eight subjects (66.7%) will be randomized to the MDMA group and four subjects (33.3%) will be randomized to the placebo group. During the study, there will be a maximum of 24 experimental sessions with MDMA, with eight sessions in each dose group, and eight experimental sessions with placebo. Observations before, during, and after experimental sessions will be compared between these groups of equal size to explore the effects of MDMA-assisted therapy in the first double-blind, randomized, placebo-controlled trial of this treatment for social anxiety in a sample of autistic adults.

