Upon enrollment, the first six subjects (Group 1) will be randomized to receive one dose of either placebo (N=2) or 75 mg MDMA (N=4). In the second experimental session one month later, Group 1 subjects randomized to MDMA will escalate to 100 mg MDMA, unless contraindicated by safety and tolerability concerns. The second six subjects (Group 2) will be randomized to receive one dose of either placebo (N=2) or 100 mg MDMA (N=4). In the second experimental session one month later, Group 2 subjects randomized to MDMA will escalate to 125 mg MDMA, unless contraindicated by safety and tolerability concerns. Subjects randomized to placebo in Group 1 and Group 2 will

receive placebo in both experimental sessions also scheduled one month apart. The blind will be maintained through the six-month follow-up for each individual subject, after which the blind will be broken. Placebo subjects will be offered an open-label extension (Stage 2) with two experimental sessions scheduled one month apart, in addition to three hour-long integrative sessions during the month after each experimental session. Stage 2 subjects will receive 75 mg MDMA in the first experimental session and will escalate to 125mg MDMA in the second experimental session, unless contraindicated by safety and tolerability concerns from other subjects in Stage 1.

During experimental sessions, there will be periods of structured and unstructured interactions. The structured interactions will be selected based on elements of therapeutic interventions that are currently in use in this population for the treatment of social anxiety and to enhance functional skills [7]. The unstructured interactions will include an array of therapeutic activities and approaches that would be appropriate for subjects to engage in during experimental sessions. All subjects will follow the same schedule of structured alternating with unstructured periods but will be able to choose from a selection of activities during each unstructured period. Examples include, but are not limited to, working with art supplies, listening to preselected music, writing in journals, silent introspection, and engaging in rapport-building interactions with researchers.

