12.0 Data Analysis

This study is primarily a safety study that will also obtain estimates of effect size comparing MDMA vs. placebo using observer-blind data from the LSAS as the primary outcome measure. MDMA doses are not expected to differ greatly in treatment outcomes and will be combined for effect size estimates. Descriptive statistics will be computed overall for MDMA and placebo, and within the MDMA dose groups for all available data from outcome measures, including minimum, maximum, average, and standard deviation. Distributional characteristics will be examined for outliers and extreme values and, if either is evident, nonparametric statistics will be utilized in the analysis. Effect size for all outcome measures will be estimated using Cohen's techniques.

The sponsor will examine MDMA and placebo groups for homogeneity through comparing demographic characteristics. There is no expectation that conditions will differ in composition by gender, race or ethnicity, duration of autism diagnosis, or presence versus absence of other permitted psychiatric disorders, such as depression. However, owing to small sample size, such variations may arise by chance. If MDMA and placebo subjects differ upon a demographic variable, then the effects of this variable will be taken into account when looking at safety analyses. No systematic differences are expected.

Primary and secondary outcome measure scores will be plotted across each time of administrations for trend analyses. The number of intervals will vary in accordance with times listed for each measure, but will include in most cases baseline, one or more times after the first experimental session, one or more times after the second experimental session and at six month follow up. Plots will be made for MDMA and placebo subjects, and if trends occur for MDMA subjects, separate exploratory plots will be made for outcome measures after 0, 75, 100 and 125 mg MDMA.

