The main estimates of effect size from blinded data will be conducted after the outcome measure assessments at the six-month follow-up are complete for all subjects. Data from all doses of MDMA during Stage 1 (n=16), to be compared with all data from placebo sessions (n=8), with each experimental session treated as an independent observation. The MDMA condition will encompass both Group 1 and Group 2 MDMA doses. Estimates of effect size will be obtained from BDI-II, STAI, PSS, IRI, RSES, ERQ, TAS-20, and QoL-Q scores collected pre-treatment, during and after each experimental session, and the follow-up period, with p value set at 0.05. Effect size will be used to determine the appropriate sample size for future studies.

Scores for BDI-II, STAI, PSS, IRI and RSES completed after each of the experimental session will be averaged to produce mean scores for these periods, including a post-experimental session 1 and post-experimental session 2 average score. BDI-II, STAI and PSS scores gathered via postal mail at monthly intervals from two to five months after the second experimental session will be averaged to produce mean scores for the follow-up period. Missing responses will be replaced with the sample average. These averages will be used for estimates of effect size.

TASIT scores will be compared assessing baseline, after experimental session 1, after experimental session 2, at integrative session six and at 6-month follow up. Correlations between TASIT scores and LSAS scores at the time point following each TASIT score will be made to see whether increased awareness of social cues is associated with reduced social anxiety. MDMA dose will be used as a covariate in order to examine the potential relationship between dose and changes in one or more variable, with dose (75, 100 or 125 mg) serving as the covariate.

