Descriptive statistics will be computed for vital signs and subjective distress during each experimental or open-label session. The sponsor will compare pre-drug and post-drug peak blood pressure, heart rate, and body temperature during and after all experimental sessions by condition and MDMA dose. Analyses will compare peak vital signs between MDMA and placebo subjects, and a separate analysis will consider the effects of dose (0, 75, 100 or 125 mg MDMA) upon vital signs.

Frequency tables will be produced on prevalence of spontaneously reported reactions and AEs. Number and severity of spontaneously reported reactions will be compared in MDMA and placebo subjects using a one-way analysis of variance (ANOVA). The effects of MDMA dose upon number and severity of spontaneously reported reactions will also be assessed. Presence and degree of exacerbated symptoms across MDMA and placebo participant will also be examined.

Perceptions of study participation will be examined at baseline, 6-month follow-up, and end of Stage 2 using the Feedback Questionnaire and a qualitative interview. The results of this qualitative analysis will inform the sponsor of expectancies and perceptions about study procedures for future protocol development. Similarly, belief of condition assignments collected during Stage 1 will be used to assess the effectiveness of the double-blind in preparation for future studies. Results from the Feedback Questionnaire and safety data will be utilized to find the appropriate active MDMA dose for future studies.

To facilitate the planning of future studies, a preliminary estimate of effect size may be performed after all the subjects have completed the outcome assessments, one month after the second experimental session, but not all subjects have completed the six-month follow-up evaluation. This preliminary estimate will consist of safety and outcome measures. Results of the preliminary estimate will have no effect on study conduct.

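### Section 2.3 promises a blinded comparison of equal-sized dose and placebo session groups, but the sizes are equal only if open-label Stage 2 sessions are pooled in

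*Protocol*

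**What the plan says.** Protocol section 2.3 sets the allocation: "Overall, eight subjects (66.7%) will be randomized to the MDMA group and four subjects (33.3%) will be randomized to the placebo group". It then gives session totals: "there will be a maximum of 24 experimental sessions with MDMA, with eight sessions in each dose group, and eight experimental sessions with placebo". The next sentence says that "Observations before, during, and after experimental sessions will be compared between these groups of equal size", and describes the purpose as exploring treatment effects in a double-blind, randomized, placebo-controlled trial.

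The doses behind those totals are in Table 1 (section 2.4) and section 4.0. In Stage 1, four Group 1 subjects get 75 mg first, and then "Group 1 subjects randomized to MDMA will escalate to 100 mg MDMA". Four Group 2 subjects get 100 mg and then 125 mg. Two subjects in each group get placebo twice. After the six-month follow-up and unblinding, placebo subjects may have open-label sessions at 75 mg and then 125 mg. Section 5.2.8 makes this stage optional.

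Section 12.0 restricts the main effect-size estimate: "Data from all doses of MDMA during Stage 1 (n=16), to be compared with all data from placebo sessions (n=8"). Its by-dose passages carry no such limit. Descriptive statistics are computed "within the MDMA dose groups for all available data from outcome measures". Peak vital signs are compared "during and after all experimental sessions by condition and MDMA dose", with a further analysis across 0, 75, 100 and 125 mg. The effect of dose on the number and severity of spontaneously reported reactions is also to be assessed.

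**The concern.** The equal sizes in section 2.3 cannot be obtained from the blinded, randomized part of the trial. If they are produced by adding Stage 2, the four session groups are not separate randomized groups. The four placebo subjects supply all of the placebo sessions, half of those at 75 mg and half of those at 125 mg. Their MDMA sessions come months later, with the treatment known. The 100 mg group has no such sessions.

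Any effect of knowing the treatment, or of the later date, would then be credited to 75 and 125 mg against both placebo and 100 mg. Section 12.0 says that safety data, with the Feedback Questionnaire, will help find the dose for future studies, so a by-dose table that mixes blinded and open-label sessions could feed that choice.

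**Working it through.** **Inputs.** Subjects per row and dose per session come from Table 1 and section 4.0. Stage 2 being optional comes from section 5.2.8.

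**Step 1: reproduce the plan's totals.** All four placebo subjects are assumed to enter Stage 2, and every escalation to go ahead.

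| | Stage 1, blinded | Stage 2, open-label | Pooled | Open-label share |
|---|---|---|---|---|
| Placebo | 4 × 2 = 8 | 0 | 8 | 0% |
| 75 mg | 4 (Group 1, session 1) | 4 | 8 | 4/8 = 50% |
| 100 mg | 4 (Group 1, session 2) + 4 (Group 2, session 1) = 8 | 0 | 8 | 0% |
| 125 mg | 4 (Group 2, session 2) | 4 | 8 | 4/8 = 50% |

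MDMA sessions: 16 blinded + 8 open-label = 24. The stated 24, and eight per group, are reproduced, but only with Stage 2 included. Stage 1 alone gives 4, 8, 4 and 8 by dose, or 16 against 8 sessions by condition.

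**Step 2: dependence on Stage 2 uptake.** If k of the four placebo subjects enter, the 75 and 125 mg groups each have 4 + k sessions, against 8 at 100 mg and 8 on placebo. For k = 0, 1, 2, 3, 4 that is 4, 5, 6, 7, 8. The open-label share k/(4 + k) is 0%, 20%, 33%, 43%, 50%. Sizes are equal only at k = 4.

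**Step 3: who is in each pooled group.** Placebo: 4 subjects, all randomized to placebo. 75 mg: 8 subjects, 4 of them randomized to placebo. 100 mg: 8 subjects, none randomized to placebo. 125 mg: 8 subjects, 4 of them randomized to placebo.

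**Step 4: bias from pooling.** Let an open-label session shift a measurement by D standard deviations. The documents give no value for D. With no true dose effect and common mean m, the pooled 75 mg mean is (4m + 4(m + D))/8 = m + D/2, and likewise at 125 mg. Placebo and 100 mg stay at m. The bias is 0 for D = 0, 0.25 SD for D = 0.5 and 0.50 SD for D = 1. It cancels between 75 and 125 mg, which have the same share.

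**Step 5: does restriction to Stage 1 suffice?** Each subject gives two Stage 1 sessions. Assume common variance s² and within-subject correlation r (also not given).

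- 75 mg against placebo: the variance of the mean difference is s²[1/4 + (1 + r)/8]. At r = 0.5 this is 0.4375s². Treating sessions as independent gives s²(1/4 + 1/8) = 0.375s², too small by a factor of 0.4375/0.375 = 1.17.
- 75 mg against 100 mg: the four Group 1 subjects are in both, so the variance is s²[1/4 + 1/8 − 2r/8]. At r = 0.5 this is 0.25s², against 0.375s² under independence, which is too large.

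The 125 mg comparisons have the same structure. A simulation of Stage 1 alone (40,000 trials, r = 0.5, no dose effect, independent-sessions t-test at 5%) gives about 7.7% false positives for 75 or 125 mg against placebo, and about 2% for either against 100 mg. A subject-level term is therefore needed with or without Stage 2.

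**Step 6: session order.** With the schedule followed, 75 mg is always the first MDMA session and 125 mg always the second; 100 mg is four of each. Dose is therefore confounded with order even within Stage 1.

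**The case against.** The strongest reply is that section 2.3 is a statement of purpose and the operative plan mostly keeps to Stage 1. That is largely right:

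- Section 3.2 sets the comparative secondary objectives in Stage 1.
- Section 12.0 limits the main estimate to Stage 1, combines doses for effect sizes, and compares the two stages separately.
- SAP 8.10.1 and 8.10.2 test change to Visit 13, and 8.10.2.1 treats crossover subjects separately.
- SAP 8.10.4 tabulates adverse events and reactions by Stage 1 group and only describes vital signs.
- SAP section 2.0 repeats the dose and allocation text of section 2.3 without the equal-size sentence.

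A reader might infer that section 12.0 plans to pool the stages by dose. The documents do not establish that. The sentence before the peak vital-sign comparison names open-label sessions alongside experimental ones, which suggests that the comparison excludes them. Yet sections 4.0 and 5.2.8 call Stage 2 sessions experimental. The text is ambiguous. The by-dose outcome summaries are descriptive, and the TASIT dose covariate follows Stage 1 time points.

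A reader might also blame pooling for any wrong error rate in session-level tests. That does not follow. 100 mg against placebo contains no open-label session, so any inflation there comes from repeated placebo sessions. Step 5 shows similar distortions in Stage 1 alone.

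Finally, an expectancy shift is less plausible for blood pressure or temperature than for reported reactions. This stands as a limit on the likely size of D. The error in section 2.3 remains.

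**Conclusion.** The point holds in a limited form. The equal-size comparison in section 2.3 is not available from blinded data: Stage 1 gives 4, 8 and 4 MDMA sessions and 8 placebo sessions. Reaching eight in each requires full uptake of an optional stage, every planned escalation, and pooling that makes half of the 75 and 125 mg sessions open-label. Under that pooling those two doses are biased by D/2 against placebo and 100 mg. D is an assumption, and the result ranges from no bias to 0.50 SD for D between 0 and 1.

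The main effect-size estimate and the SAP primary analysis are untouched by pooling. The exposure is the section 2.3 statement and the by-dose vital-sign and reaction analyses in section 12.0, where inclusion of Stage 2 is unclear. In an exploratory pilot this is a low-priority correction.

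**What to change.** In section 2.3, replace the equal-size claim with the Stage 1 counts (75 mg 4, 100 mg 8, 125 mg 4, placebo 8 sessions from four subjects), and state that up to 8 of the 24 MDMA sessions are open-label.

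In section 12.0, state that comparative by-dose analyses use blinded Stage 1 sessions with a subject-level random effect. Show Stage 2 separately, labelled open-label. If the stages are pooled for safety, keep the random effect and add an open-label indicator. Note that dose and session order are confounded in Stage 1, so by-dose differences cannot be read as dose effects alone.

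The cost is wording. The downside is that the 75 and 125 mg comparative cells fall from 8 to 4 sessions, which is the blinded information the design provides. No Stage 2 data are lost from reporting.

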2.4 Rationale of Dose Selection

The MDMA doses of 75mg and 125mg to be used in this study have been used in previous and ongoing MAPS-sponsored studies in the U.S., Switzerland, and Israel [81, 82]. Previous researchers have also used doses within this range up to 225mg [75, 76, 78, 79, 91, 99, 116, 124-126]. Prior to the scheduling of MDMA, similar doses and regimens were used in psychotherapy [36, 62, 64]. Each MDMA dose is expected to produce the commonly reported effects of MDMA.

Anecdotal reports suggest a potential for increased sensitivity to the effects of MDMA in autistic individuals who experience sensory hyperarousal [68]. Therefore, subjects will only receive a single administration of MDMA during experimental sessions, and the lower 75 mg and 100 mg doses will be administered to assess for enhanced sensitivity during the first experimental session to subjects randomized to MDMA. MDMA subjects will only escalate to a 25mg higher dose in the second experimental session that they receive one month later. If any subjects within each dose group experience a drug-related SAE, the dose escalation procedure will not continue for remaining subjects in the same dose group in the interest of subject safety. If this occurs, the institutional Data Safety Monitor and Sponsor Medical Monitor will be consulted to determine the course of action. Any subject who experiences a drug-related SAE will be excluded from any additional experimental sessions, but will continue with non-drug therapy and follow-up assessments whenever possible.

Table 1. Dose Regimen

Group # /Randomization /Sample	Stage 1		Stage 2 Open-Label Extension	
	Session 1 Month 1	Session 2 Month 2	Session 1 Month 6	Session 2 Month 7
Group 1 active N=4	75 mg	100 mg	N/A	N/A
Group 1 placebo N=2	Placebo	Placebo	75 mg	125 mg
Group2 active N=4	100 mg	125 mg	N/A	N/A
Group 2 placebo N=2	Placebo	Placebo	75 mg	125 mg

3.0 Protocol Objectives

The main objective of this study is to collect safety data to examine whether MDMA-assisted therapy will be tolerated and to estimate effect size of symptom reduction in social anxiety that is common in the adult autistic population as evaluated by standard clinical measures.

3.1 Primary Objective:

To estimate effect sizes of social anxiety symptom reduction between MDMA and placebo, as measured by the clinician-administered LSAS administered by a blinded IR, at baseline, one day, two weeks, and one month after each experimental session, and at 6-month follow-up.

3.2 Secondary Objectives:

The following objectives will compare MDMA subjects to placebo subjects in Stage 1:

- To assess effects on levels of OT, AVP, and CORT in peripheral blood at baseline, once during each experimental session between hours 2 – 3, one month after the second experimental session, and at 6-month follow-up.
- To assess effects on social perception using The Awareness of Social Inference Test (TASIT) at baseline, once during each experimental session between hours 2 – 3, one month after the second experimental session, and at 6-month follow-up.
- To assess effects on emotion labeling using the Toronto Alexithymia Scale-20 (TAS-20) at baseline, one month after each experimental session, and 6-month follow-up.
- To assess effects on emotion regulation using the Emotion Regulation Questionnaire (ERQ) at baseline, one month after each experimental session, and 6-month follow-up.
- To assess effects on depression symptoms as measured by the Beck Depression Inventory-II (BDI-II) at baseline, one day, two weeks, one month after each

- experimental session, monthly by mail during the 5 months leading up to the 6-month follow-up assessment.
- To assess effects on perceptions of stress as measured by the Perceived Stress Scale (PSS) at baseline, within 24 hours after each experimental session, one month after each experimental session and monthly by mail leading up to the 6-month follow-up assessment.
 - To assess effects on four aspects of empathy, as measured by the Interpersonal Reactivity Index (IRI) at baseline, within 24 hours after each experimental session, one month after each experimental session, and at the 6-month follow-up assessment.
 - To assess effects on self-esteem as measured by the Rosenberg Self-Esteem Scale (RSES) at baseline, within 24 hours after each experimental session, one month after each experimental session, and at the 6-month follow-up assessment.
 - To assess effects on state and trait anxiety as measured by the State-Trait Anxiety Index (STAI Form Y) at baseline, one day, two weeks, and one month after each experimental session, and monthly by mail leading up to the the 6-month follow-up assessment.

The following objectives will compare effects in specified subjects:

- To conduct a within-subject comparison of Stage 1 LSAS outcomes to Stage 2 open-label LSAS outcomes.
- To conduct a hierarchical regression analysis using condition assignment in Stage 1 and TAS-20 scores and OT, AVP, and CORT at baseline as predictors and LSAS outcomes as dependent variables.

The following objectives will include exploratory analyses intended to inform protocol design:

- To assess the ability of the investigators and subjects to accurately guess condition assignment in Stage 1.
- To assess perceptions about dose and study procedures at baseline and 6-month follow-up using a qualitative interview and feedback questionnaire.
- To determine feasibility of recruiting, testing and treating subjects on the autism spectrum with MDMA-assisted therapy as measured by enrollment rates, dropout rates, and completion of assessments and other study-related procedures.

3.3 Safety Objectives:

The safety of subjects will be assured during and after the experimental sessions by assessing physiological effects, psychological distress, AEs, spontaneously reported reactions and suicidality.

- Vital signs (BP, HR, temp.) will be measured at baseline and every hour during experimental sessions until they return to baseline.
- Participant distress will be measured by the Subjective Units of Distress (SUD) scale at baseline and every hour during experimental sessions until return to baseline.

- Risk of suicide will be measured by the Columbia Suicide Severity Rating Scale (CSSRS) during all in person visits, as well as twice during each experimental session at two hours after drug administration and the end of the experimental session, and on Day 2 and Day 7 after each experimental session.
- SAEs and AEs will be assessed throughout the study and spontaneously reported reactions, defined as expected AEs, will be assessed during each experimental session and for seven days after each experimental session, or until resolution.
- In addition to spontaneously reported reactions, symptoms specific to the study population will be collected at baseline and tracked throughout the study.

